# 9.2.2 Multidimensional flow cytometry (eligibility), E-selectin ligand expression, and gene expression profiling shipments

Samples should be shipped ambient on the day of collection. Samples can be accepted Monday through Saturday.

Hematologics, Inc. [name] Contact: [name] E-mail: [contact] [contact] or [contact]

Prior to shipping samples an email notification should be sent to [contact], including the protocol number, subject ID number and carrier tracking number.

Each sample should be labeled with collection date and time obtained (for fresh samples), protocol number, subject ID number, and site code. Corresponding information must be placed on the Hematologics Laboratory Test Requisition Form. This form must be scanned and emailed to [contact] and study coordinator, the original retained at the site, and a copy included in the packaging.

# 10. STUDY CALENDAR AND REQUIRED ROUTINE TESTING/CLINICAL EVALUATIONS

Table 8. Study Calendar						D	ay Relati	ive to Tra	nsplant			
						+30	+50	+100	+180	+365	+730	
Routine Testing and Clinical Evaluations	Baseline a	-8	-4	0	+14	+/- 5 days	+/-7 days	+/- 7 days	+/- 14 days	+/- 30 days	+/- 90 days	InForm Timepoints
Informed consent/assent	X											Baseline
Demographics	X											Baseline
Medical history	X	X										Baseline, Day -8
Physical exam	Xb	X		X		X		X		X	Х	Baseline, Days -8, 0, +30, +100, +365, and +730
Performance status	X	X		X		X		X		X	Х	Baseline, Days -8, 0, +30, +100, +365, and +730
Serum Pregnancy Test	X											Baseline
Estimated GFR	X											Baseline
Echocardiography	X			1								Baseline
Pulmonary Function c	X			1								Baseline
Testing Hep B and Hep C infection	X											Baseline
PK collection d		Х	X									Day +30
E-selectin ligand BM collection d	X											Baseline
Disease re-evaluation e	X					X						Baseline, Day +30
Blood chemistries f	X	Twice weekly through Day +50 Per institutional guidelines				nes	Baseline, Day +30, Day +100					
CBC	X			2			itional gi			0		Baseline, Day +30, Day +100
Coagulation studies	X											Baseline
Urinalysis	X											Baseline
TNC dose, CD3+ and CD34+ counts on infused product				X								Day 0
Peripheral blood chimerism g						X						Day +30
RRT evaluation		D0 - D+30 Daily while inpatient, or 3x weekly if outpatient						Day +30				
MBI-LCBI			D0 - D+30 Daily while inpatient, or 3x weekly if outpatient				Day +30					
VOD/SOS evaluation				D0 while	- D+30 inpatien	Daily t, or 3x						Day +30
Oral and Intestinal Mucositis Evaluation				Dail	y D0 - +14							Day +30
Acute and Chronic GVHD Evaluation				1	Per ins	titutiona	l guidelin	es through	h Day +36	5		All
Relapse and Survival			Pe	er institu				Day +730				All

a. All clinical and laboratory studies to determine eligibility must be performed within 28 days prior to enrollment unless otherwise indicated in Section 3

b. Baseline includes height and weight

c. For patients developmentally unable to perform pulmonary function tests, documentation of oxygen saturation on room air will suffice

d. Refer to Table 7 for timing and other instructions for collection

e. Includes marrow testing and re-assessment of any extramedullary disease, including imaging and/or CSF, as indicated, +/- 5 days from Day +30 assessment

f. Creatinine, bilirubin, alkaline phosphatase, ALT, AST, and other blood chemistries, after Day +50 obtained per institutional practice g. Sorted for T cells (CD3+) and myeloid cells (CD3+ or CD15+), +/- 5 days

## 10.1 Pre-Transplant

- 10.1.1 As per eligibility criteria. See section 3.
- 10.1.2 Medical history, physical exam, performance status on Day -8.
- 10.1.3 PK collection and E-selectin ligand BM collection as per Table 7.

## 10.2 Post-Transplant Laboratory Testing

- 10.2.1 Total nucleated cell count, CD3+, and CD34+ counts on the infused product on Day 0.
- 10.2.2 Physical exam and performance status on Day 0.
- 10.2.3 Peripheral blood chimerism analysis to assess donor engraftment at Day +30 +/- 5 days Samples shall be sorted for T cells (CD3+) and myeloid cells (CD33+ or CD15+).
- 10.2.4 Disease re-evaluation will be performed at Day +30 +/- 5 days. It should include marrow testing and re-assessment of any extramedullary disease, including imaging and/or CSF, as indicated.
- 10.2.5 Complete blood counts with a differential shall be obtained according to institutional practice to monitor myeloid recovery and to determine transfusion needs.
- 10.2.6 Creatinine, bilirubin, alkaline phosphatase, ALT, AST, and other blood chemistries shall be performed at least twice weekly through Day +50 and otherwise obtained according to institutional practice.
- 10.2.7 Routine clinical monitoring for CMV and other infections shall be performed according to institutional practice.
- 10.2.8 Immune reconstitution testing shall be performed according to institutional practice.

#### **10.3** Other Post-Transplant Evaluations

10.3.1 Mucosal barrier injury-associated laboratory-confirmed bloodstream infection (MBI-LCBI)

MBI-LCBI will be assessed from day 0 through Day +30 and defined according to CDC criteria: https://www.cdc.gov/nhsn/pdfs/pscmanual/4psc\_clabscurrent.pdf\*-

Oral mucositis severity will be assessed daily from Day 0 through Day +14, using CTCAE v5 criteria.

Intestinal mucositis severity will be assessed daily from Day 0 through Day +14, using

CTCAE v5 criteria for enterocolitis.

10.3.2 Hepatic veno-occlusive disease (VOD)/sinusoidal obstruction syndrome (SOS) will be will be diagnosed and graded according to the pediatric (<18 years) and adult (≥18 years) European Society for Blood and Marrow Transplantation (EBMT) criteria (Appendix C).

All reported cases of sinusoidal obstruction syndrome will be adjudicated (diagnosis and grading) by a physician with expertise in this area.

- 10.3.3 Acute GVHD will be assessed through 1 year according to the Blood and Marrow Transplant Clinical Trials Network Manual of Procedures. https://web.emmes.com/study/bmt2/public/MOP/BMTCTNTechnicalMOPv3.pdf
- 10.3.4 Physical exam and performance status collected at least on Day 0, +30, +100, +365, and +730. May be collected more often as per institutional guidelines.
- 10.3.5 Chronic GVHD will be assessed through 1 year using the NIH consensus criteria.
- 10.3.6 Relapse will be assessed per institutional guidelines through 2 years post transplant.

# **11. MEASUREMENT OF EFFECT**

#### **11.1 Refractory Disease**

Applies to patients who were not in remission at the time of transplant.

At Day +30 (+/-5 days) post-transplant disease evaluation, there is persistence of >1% leukemic blasts by multidimensional flow cytometry (MDF) or there is persistence of EMD.

## 11.2 Leukemic Relapse

Applies to patients who were in remission at the time of transplant and pateints not in remission at the time of transplant who achieve remission post-transplant (based on day +30 assessment)

11.2.1 Bone Marrow Relapse

Defined in accordance with the Children's Oncology Group's AAML1831 trial protocol criteria:

A single bone marrow sample (aspirate or biopsy) showing  $\geq$ 5% leukemic blasts confirmed by flow cytometry, FISH testing, ICH, or other molecular method.

OR

A single bone marrow sample with at least two tests showing  $\geq 1\%$  leukemic blasts.

Examples of tests include:

- Flow cytometry showing leukemia  $\geq 1\%$  by multidimensional flow cytometry (MDF) in a CLIA-approved laboratory.
- Karyotypic abnormality (must display at least 1 metaphase similar/identical to diagnosis; central cytogenetic review by COG required).
- FISH abnormality identical to one present at diagnosis (must be above level of sensitivity of specific FISH probe; central cytogenetic review by COG required).
- PCR or NGS-based demonstration of validated pathogenic leukemogenic lesion (e.g., fusion, mutation) in a CLIA-approved laboratory that matches initial diagnosis and is quantifiable as ≥1%.

## OR

Two serial marrows with at least two tests showing a one log increase of leukemic involvement with the second tests quantified as  $\ge 0.1\%$ . Examples of tests include:

- MDF in CLIA-approved laboratory
- PCR or NGS-based demonstration of validated leukemogenic lesion (e.g., fusion, mutation) that matches diagnosis and is quantifiable where the positive result is at or above the assay sensitivity and meets the criteria above (one log increase and second test quantified as  $\geq 0.1\%$ )

# 11.3 Extramedullary Relapse

Defined as radiographic or biopsy proven extramedullary disease after documented CR or evidence of CSF recurrence.

## 11.3.1 CNS Relapse

A single CSF sample with CNS3 status (Rel-CNS3a/b).

## OR

Clinical signs of CNS leukemia such as facial nerve palsy, brain/eye involvement, or hypothalamic syndrome (Rel-CNS3c). Competing explanations for clinical symptoms should be ruled out.

OR

Radiographic evidence of an intracranial, intradural mass consistent with a chloroma (Rel-CNS3c).

Equivocal CNS Relapse (Eq-CNS) A single CSF sample with CNS2 status

In the case of equivocal relapse, CSF evaluation should be repeated at least 1 week and at most 4 weeks later. For repeat CSF assessment, flow cytometric testing is strongly recommended and FISH (if a diagnostic FISH marker is available) should be sent

To convert to definitive relapse, the repeat CSF or clinical status must:

- Meet criteria for definitive relapse (Rel-CNS3a/b/c)
- Re-demonstrate CNS2 status, but with myeloblasts confirmed by flow cytometry and/or FISH (Rel-CNS2)
- For Rel-CNS2, the two CSF samples MUST BE CONSECUTIVE

# **12. DATA REPORTING / REGULATORY REQUIREMENTS**

Adverse event lists, guidelines, and instructions for AE reporting can be found in Section 7 (Adverse Events: List and Reporting Requirements).

# 12.1 Data Reporting

12.1.1 Method

The DF/HCC Office of Data Quality (ODQ) will collect, manage, and perform quality checks on the data for this study.

12.1.2 Responsibility for Data Submission

Investigative sites are responsible for submitting data and/or data forms to the Office of Data Quality (ODQ). All data will be entered within two weeks of the indicated time point.

## 12.2 Data Safety Monitoring

This study will be centrally reviewed by the Data Safety and Monitoring Committee (DSMC) of the Pediatric Transplant and Cellular Therapy Consortium (PTCTC). This DSMC is chartered to monitor trials enrolling both children and adult patients. The DSMC is a standing committee, composed of a chair, patient advocate, biostatistician, nurse representative and 2 bone marrow transplant physicians with procedures and processes as defined in the PTCTC DSMC Charter. The DSMC will review the study protocol prior to study activation and IRB review, and will continue to review the study on a regular basis according to the committee rules. The DSMC will meet at regular intervals to review all adverse events and deaths and determine whether any patient safety problems necessitate protocol modifications or discontinuation of the trial. The DSMC will also meet on an ad hoc basis to review the results of interim analyses or if unexpected safety events occur that may necessitate study suspension or closure. The DSMC will discontinue the review of outcomes when administration of the study product has ended for all

subjects. The DSMC has the authority to unblind study personnel prior to study closure if, in their opinion, doing so will be critical to patient safety.

Before each regularly scheduled DSMC meeting, the study coordinator will submit a report including tabular summaries of all reported SAEs, AEs and deaths on study to date. The report will also include a brief summary of each previously unreported SAE and death, including an assessment of whether the event was unexpected or related to the study. If the DSMC recommends protocol or informed consent changes during the study, the recommendations will be reviewed by the Protocol Chair and incorporated into the protocol as deemed appropriate. The protocol with incorporated changes will be distributed to the participating PIs after approval by the Dana Farber Cancer Institute IRB. It is the responsibility of each Transplant Center PI to forward the distributed communications from the DSMC to their local IRB.

## **12.3** Multicenter Guidelines

This protocol will adhere to DF/HCC Policy MULTI-100 and the requirements of the DF/HCC Multi-Center Data and Safety Monitoring Plan. The specific responsibilities of the Sponsor-Investigator, Coordinating Center, and External Sites and the procedures for auditing are presented in Appendix B.

# **13. STATISTICAL CONSIDERATIONS**

This is a prospective, multicenter, single treatment arm phase 1/2 clinical trial. Phase 1 will proceed according to a standard 3+3 design. Phase 2 will expand enrollment to N=20 patients at the RP2D identified in Phase 1 to confirm safety and estimate preliminary efficacy. In phase 2, interim monitoring will be performed for transplant-related mortality within 100 days of transplant (see section 13.5).

## **13.1** Definition of Evaluability

13.1.1 Definition of Evaluability for Dose Escalation Evaluation (Phase 1)

Eligible patients who are evaluable for the dose-determining analysis are those who either: A) meet the following minimum exposure criterion and complete the DLT observation period without experiencing a DLT;

or

B) receive at least 1 dose of uproleselan and experience a DLT during the DLT observation period.

A patient is considered to have met the minimum exposure criterion if he/she received at least 10 of the 12 of planned doses of uproleselan in the first cycle of dosing. Patients who do not meet criteria for inclusion in the dose-determining analysis population will be replaced in the study accrual. 13.1.2 Definition of Evaluability for estimation of efficacy (Phase 2)

Eligible patients will be evaluable for estimation of efficacy if they have received at least one dose of uproleselan at the RP2D. Patients who do not receive any uproleselan will be replaced in the trial accrual.

13.1.3 Patients to be included in safety analysis (Phase 1 and 2)

Eligible patients will be included in reporting toxicities if they have received at least one dose of uproleselan.

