# 7.2 Adverse Event Characteristics

Investigators are to provide the following adverse event characteristics for all adverse events experienced from the time of enrollment through when the participant is taken off study (see section 5.7).

In this trial, in which uproleselan, an investigational agent is being administered in combination with commercial agents (fludarabine, clofarabine, and busulfan), the combination is considered investigational and expedited reporting of adverse events will follow the guidelines for investigational agents. Attribution and expectedness for adverse events will not be evaluated with respect to uproleselan alone; these evaluations will be done based on the combination of uproleselan and the above commercial agents as a single study treatment.

**CTCAE term (AE description) and grade:** The descriptions and grading scales found in the revised NCI Common Terminology Criteria for Adverse Events (CTCAE) version 5.0 will be utilized for AE reporting. All appropriate treatment areas should have access to a copy of the CTCAE version 5.0. A copy of the CTCAE version 5.0 can be downloaded from the CTEP web site http://ctep.cancer.gov/protocolDevelopment/electronic\_applications/ctc.htm.

**Expectedness** of the AE: In addition to term, grade, attribution, and seriousness, are to be designated as "expected" or "unexpected." For the purposes of determining expectedness, all the adverse events listed in Sections 7.1.1-7.1.8 or in the consent documents are to be considered expected. Any adverse events not listed in sections Sections 7.1.1-7.1.8 or in the consent documents are to be considered unexpected.

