# 7.5 Expedited Reporting

All SAEs must be reported to the Sponsor Investigator immediately, no later than 24 hours of first becoming aware of the event. All SAEs must be reported despite grade or whether or not considered drug related, including those listed in the protocol or investigator brochure and must include an assessment of whether there is a reasonable possibility that the drug caused the event.

The Sponsor Investigator ([name]) and DFCI study team

([contact]) should be informed by email within 24 hours of all SAEs that occur after the patient has provided informed consent, during treatment, or until the participant is taken off study. In the event that the participating investigator does not become aware of the SAE immediately, the participating investigator is to report the event within 24 hours of learning of it and document the time of his or her first awareness of the event.

The study site will have 5 business days from the discovery of the SAE to send a complete expedited report to the Sponsor Investigator.

In addition to SAEs, per DFCI's Expedited Reporting requirements, the following events also require expedited reporting unless they are specifically excluded in Section 7.3:

- Unexpected grade 2 or 3 with a possible, probable, or definite attribution
- Unexpected grade 4 toxicities regardless of attribution
- Dose limiting toxicities that are described in section 5.3

*Pregnancies*: To ensure patient safety, each pregnancy in a patient on study treatment must be reported to the Sponsor Investigator. Pregnancy follow-up should include an assessment of thepossible relationship to the study treatment any pregnancy outcome. Any SAE experienced during pregnancy must be reported. Additionally, pregnancy outcomes should be collected for the female partners of any male study participants. Consent to report information

regarding these pregnancy outcomes should be obtained from the pregnant partner. Sites should follow their institutional policies regarding consenting pregnant partners.

*Unanticipated problems or life-threatening complications:* In the event of an unanticipated problem or life-threatening complications that places subjects or other persons at greater risk of harm than previously recognized occurs, treating investigators must immediately notify the Sponsor-Investigator.

Sponsor-Investigator contact information:

- [name]
- Email: [name]
- [contact]
- DFCI lead study coordinator or study team: [contact]

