## 13.6 Analysis of Primary Endpoints

To address primary objective in section 1.3 Phase 1, the RP2D will be identified through the application of the 3+3 design. Accrual will be temporarily suspended after the enrollment of each cohort of 3 patients on a dose level, until all 3 patients have either completed the DLT observation period (30 days) or experienced a DLT.

To address primary objective in section 1.3 Phase 2, all observed toxicities will be summarized

using frequencies, proportions, and 95% confidence intervals by type (organ affected or laboratory determination), severity (by CTCAEv5.0), attribution, and expectedness. Only the maximum grade for each type of toxicity will be tabulated for each patient.

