### **Eligibility Exceptions**

No exceptions to the eligibility requirements for a protocol without IRB approval will be permitted. All External Sites are required to fully comply with this requirement. The process for requesting an eligibility exception is defined below.

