## Definitions

Protocol Deviation: Any departure from the defined procedures set forth in the IRB-approved protocol which is *prospectively approved* prior to its implementation.

Protocol Exception: Any protocol deviation that relates to the eligibility criteria, e.g. enrollment of a participant who does not meet all inclusion/exclusion criteria.

Protocol Violation: Any protocol departure that was not *prospectively approved* by the IRB prior to its initiation or implementation.

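### Section 13.1.3 defines the safety set by eligibility as well as exposure, so a dosed patient who proves ineligible is left out of the toxicity summaries

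*Protocol*

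**What the plan says.** Section 13.1.3 of the protocol sets the population for toxicity reporting in both phases: "Eligible patients will be included in reporting toxicities if they have received at least one dose of uproleselan". Two conditions must be met, eligibility and at least one dose.

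Appendix B leaves a route by which a patient who fails a criterion can be treated. Under Eligibility Exceptions it says: "No exceptions to the eligibility requirements for a protocol without IRB approval will be permitted". Its Definitions describe an exception as: "Any protocol deviation that relates to the eligibility criteria, e.g. enrollment of a participant who does not meet all inclusion/exclusion criteria".

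Section 13.6, on the phase 2 primary objective, says that "all observed toxicities will be summarized" and names no population.

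The operational safety sections carry no eligibility limit:

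- Section 7.2: "Investigators are to provide the following adverse event characteristics for all adverse events experienced from the time of enrollment".
- Section 7.5: "All SAEs must be reported despite grade or whether or not considered drug related".
- Section 12.2 gives the monitoring committee tables of all reported SAEs, AEs and deaths.
- The TRM and RRT rules in section 13.5 refer to the 20 patients treated at the RP2D and do not mention eligibility.

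**The concern.** A safety set is normally defined by exposure alone, because a toxicity in a treated patient is information about the treatment whether or not the patient met every entry criterion. Here safety is the primary objective of both phases, and the primary endpoint in each is the occurrence of a DLT (section 13.2.1). A rule that can remove a dosed patient from the toxicity summaries therefore touches the main result.

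The protocol itself foresees enrolled patients who do not meet all criteria, and nothing in section 13 brings them back into the safety set. Their events would be collected and shown to the monitoring committee, yet be absent from the toxicity report. With about 20 patients at the RP2D, one patient is visible in the estimate.

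**Working it through.** **Who is in, by section**

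| Place in protocol | Population | Eligibility required? |
|---|---|---|
| 7.2, 7.5 | adverse events from enrollment; all SAEs | no |
| 12.2 | all reported SAEs, AEs and deaths | no |
| 13.1.3 | at least one dose of uproleselan | yes |
| 13.5 (TRM, RRT) | 20 patients treated at the RP2D | not stated |
| 13.6 | all observed toxicities | not stated |

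A patient enrolled under an approved exception fails a criterion by the Appendix B definition. If that patient is dosed, rows 1 and 2 include the patient and row 3 does not. Row 5 depends on whether 13.6 is read through 13.1.3. As 13.1.3 is the only definition of the safety set, that is the natural reading.

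**The plan's own precision figure**

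Inputs from section 13.3: 20 evaluable patients and an observed DLT proportion of 0.20, which is 4/20. The exact (Clopper-Pearson) 95% limits are the 0.025 quantile of Beta(x, n − x + 1) and the 0.975 quantile of Beta(x + 1, n − x). With x = 4 and n = 20 these are 0.0573 and 0.4366, a width of 0.3793. The stated 0.379 is reproduced.

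**Effect of leaving out treated patients**

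The documents give no number of ineligible treated patients. As an assumption, take 1 or 2 of them in addition to 20 eligible patients with 4 DLTs.

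| Ineligible patients treated | Their DLTs | All dosed patients (exact 95% CI) | Eligible only (exact 95% CI) |
|---|---|---|---|
| 0 | 0 | 4/20 = 20.0% (5.7% to 43.7%) | the same |
| 1 | 0 | 4/21 = 19.0% (5.4% to 41.9%) | 4/20 = 20.0% (5.7% to 43.7%) |
| 1 | 1 | 5/21 = 23.8% (8.2% to 47.2%) | 4/20 = 20.0% |
| 2 | 0 | 4/22 = 18.2% (5.2% to 40.3%) | 4/20 = 20.0% |
| 2 | 2 | 6/22 = 27.3% (10.7% to 50.2%) | 4/20 = 20.0% |

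Leaving out a patient with a DLT lowers the estimate: by 23.8 − 20.0 = 3.8 percentage points for one, and by 27.3 − 20.0 = 7.3 for two. Leaving out a patient without a DLT raises it slightly.

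**Could the stopping rules be affected?**

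The rules turn on 2 versus 3 events in 20. The chance of exactly 3 is 1140 p³(1 − p)¹⁷, which is 0.190, 0.243 and 0.134 at p = 0.10, 0.15 and 0.25. For an omission to move the count from 3 to 2, the omitted patient must be one of the three. If one of the 20 is ineligible and at the same risk as the others, the joint probability is 3/20 of those values: 0.190 × 0.15 = 2.9%, 0.243 × 0.15 = 3.6% and 0.134 × 0.15 = 2.0%. These must be multiplied again by the unknown chance that an ineligible patient is treated at all. They would apply only if the rules were restricted to eligible patients, which section 13.5 does not say.

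**The case against.** Much can be said for leaving the plan alone. Eligibility is reviewed centrally before enrollment, with source documents, and treatment may not start until registration and enrollment are confirmed (section 4). Exceptions need IRB approval. Treated ineligible patients should therefore be rare. The protocol also never says outright that a patient with an approved exception is analysed as ineligible; that follows only from the Appendix B definition. These points limit the likely size of the problem. They do not remove the gap in the wording, which also covers a patient found ineligible after dosing.

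Four stronger readings are tempting and should not be drawn.

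- A reader might infer that such a patient disappears from safety oversight. Sections 7.2, 7.5 and 12.2 show otherwise.
- A reader might infer that 13.1.3 alters the TRM and RRT decisions, and cite 13% to 24% as the chance of a reversal. Those rules refer to patients treated at the RP2D. The only link to eligibility is indirect: section 13.3 calls the 20 patients evaluable, and section 13.1.2 defines evaluability for efficacy among eligible patients. The 13% to 24% is only the chance of exactly three events. Reaching three suspends enrollment so that the committee can consider termination; it does not end the trial automatically.
- A reader might infer that the omission biases toxicity downward because ineligible patients have worse organ function. Some criteria concern organ function, but others concern age, weight, disease status, donor match and testing windows. The documents do not establish a direction.
- A reader might want section 13.1.1, which opens "Eligible patients who are evaluable for the dose-determining analysis are those who either", changed so that a DLT counts in any dosed patient. That edit is not free of cost. If eligibility still applied to patients without a DLT, ineligible patients could enter the 3+3 only as events, which would tilt it towards de-escalation or termination. Whether they should inform dose finding is a design choice, not an error.

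**Conclusion.** The point holds for the toxicity summaries. Section 13.1.3 adds a condition that a safety set should not have, the protocol provides a route by which a dosed patient can fail it, and section 13.6 promises a summary of everything observed. That sections 13.1.3 and 13.6 pull apart is clear from the text. That a patient with an approved exception counts as ineligible is an inference from the Appendix B definition, though a close one.

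The size is small and conditional. It is zero if no ineligible patient is treated. With one such patient who has a DLT, and 4 DLTs among 20 eligible patients, the reported proportion would be 20.0% instead of 23.8%. The number of such patients and their event rate are assumptions, because the documents give neither. The correction is still worth making, because safety is the primary question and the change is trivial.

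**What to change.** Delete the word Eligible from section 13.1.3, so that the safety set is all patients who receive at least one dose of uproleselan, regardless of eligibility. State in section 13.6 that its summaries use this set.

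Add one sentence to section 13.5 confirming that the TRM and RRT rules count every patient treated at the RP2D, as their wording already implies.

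An eligible-only toxicity summary may be kept as a sensitivity analysis. No change to section 13.1.1 is proposed.

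The cost is a one-word deletion and two clarifying sentences. No new data are needed, since section 7 already collects the events. The planned sample size does not change.
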